#### Other baseline characteristics

Other baseline characteristics include body mass index (BMI) in kg/m² (quantitative and qualitative variable:  $<30, \ge30$ ), weight (quantitative and qualitative variable:  $<50, \ge50$  to  $>70, \ge70$  to <100 and  $\ge100$ ) (at parent baseline and OLE baseline), smoking status and alcohol habits at parent baseline.

Glycated haemoglobin A1c (HbA1c) (quantitative and qualitative variable: <5.7%,  $\ge5.7\%$  to <6.5%,  $\ge6.5\%$ ), high sensitivity C-reactive protein (hs-CRP) will be also summarized at parent baseline.

Efficacy lipid parameters (quantitative variables for all efficacy parameters and the following qualitative variables) will be also summarized at parent and OLE baselines (see definitions in Section 2.1.1):

- calculated LDL-C: <70, ≥70 to <100, ≥100 to <130, ≥130 to <160, ≥160 to <190, ≥190 mg/dL, i.e <1.81, ≥1.81 to <2.59, ≥2.59 to <3.37, ≥3.37 to <4.14, ≥4.14 to <4.91, ≥4.91 mmol/L,
- HDL-C: <40,  $\ge 40$  mg/dL, ie <1.04,  $\ge 1.04$  mmol/L
- Fasting TGs: <150, ≥150 to <200, ≥200 mg/dL, category ≥150 mg/dL (mixed dyslipidaemia) will be also displayed, i.e. <1.7, ≥1.7 to <2.3, ≥2.3 mmol/L
- Lp(a):  $<30, \ge 30$  to  $<50, \ge 50$  mg/dL, category  $\ge 30$  mg/dL will be also displayed, i.e. <0.3,  $\ge 0.3$  to  $<0.5, \ge 0.5$  g/L

Any technical details related to computation, dates, and imputation for missing dates are described in Section 2.5.

#### 2.1.2 Prior or concomitant medications

All medications taken at the time of entry into the OLE study (including those taken during the parent study and still ongoing at the time of entry in the OLE study) and until the end of the OLE study, including lipid modifying therapies and CV medications are to be reported in one of the following specific case report form pages:

- Previous and concomitant statin drugs;
- Previous and concomitant lipid lowering drugs (other than statins);
- Previous and concomitant CV medications;
- Other previous and concomitant medications (other than statin, lipid lowering drugs and CV drugs).

All medications will be coded using the World Health Organization-Drug Dictionary (WHO-DD) using the version currently in effect at Sanofi at the time of database lock.

- Prior medications at entry into the parent study are those the patient used within 3 months prior to screening visit and prior to first double-blind IMP administration. Prior medications can be discontinued before first administration or can be ongoing during treatment phase.
- Prior medications at entry into the OLE are those the patient used within 3 months prior to first open-label IMP administration. They can be discontinued before the first IMP administration in OLE or can be ongoing during OLE.
- Concomitant medications are any treatments received by the patient concomitantly with the open-label IMP, from first open-label IMP to the last open-label IMP injection +70 days. Concomitant medications do not include medications started during the post-treatment period (as defined in the observation period in Section 2.1.4).
- Post-treatment medications are those taken by the patient in the period starting from 71 days after the last open-label IMP injection and ending when the patient terminates the study.

Any technical details related to computation, dates, imputation for missing dates are described in Section 2.5.

# 2.1.3 Efficacy endpoints

Efficacy parameters include lipid parameters ([ie], [Total-C], calculated LDL-C, [HDL-C], [TGs], non-HDL-C, [Apo B], Apo A-1, ratio Apo B/Apo A-1, [Lp (a)]). All these parameters are measured or calculated by a Central Laboratory, for both scheduled and unscheduled time points. Calculated LDL-C is obtained using the Friedewald formula. Non-HDL-C is calculated by subtracting HDL-C from the Total-C. If TG values exceed 400 mg/dL (4.52 mmol/L), the LDL-C is measured by the Central Laboratory (via beta quantification method) rather than calculated. All measured LDL-C values provided by the Central Laboratory will not be used for the analysis of calculated LDL-C endpoints.

Unless otherwise specified, all lipid values (scheduled or unscheduled, fasting or not fasting) may be used to provide a value for the efficacy endpoints. All measurements, scheduled or unscheduled, fasting or not fasting, will be assigned to analysis windows defined in Section 2.5.4, Table 1 in order to provide an assessment for each time point when the lipid values were to be collected as per protocol. For TGs, only fasting measurements will be used. Measurements with missing fasting status will be excluded from the analyses.

For all time points post open-label baseline, the value used for the analyses at a given time point is the value obtained within the corresponding analysis window.

# 2.1.3.1 Primary efficacy endpoints

No primary efficacy endpoints are defined since the primary objective is dedicated to safety.

# 2.1.3.2 Secondary efficacy endpoints

The secondary efficacy endpoints are:

- The percent change in calculated LDL-C from baseline of the parent study over time in the OLE study, in the mITT population, using all LDL-C values during the efficacy treatment period defined in Section 2.3.1 (on-treatment estimand).
- The absolute change in calculated LDL-C (mg/dL and mmol/L) from baseline of the parent study over time in the OLE study (on-treatment estimand).
- The proportion of patients reaching calculated LDL-C <100 mg/dL (2.59 mmol/L) over time in the OLE study (on-treatment estimand).
- The proportion of patients reaching calculated LDL-C <70 mg/dL (1.81 mmol/L over time in the OLE study (on-treatment estimand).
- The proportion of patients with calculated LDL-C <70 mg/dL (1.81mmol/L) and / or ≥50% reduction in calculated LDL-C from baseline of the parent study (if calculated LDL-C≥70 mg/dL [1.81mmol/L]) over time in the OLE study (on-treatment estimand).
- The percent change in non-HDL-C, total-C, HDL-C, fasting TGs, Lp(a), Apo B, and Apo A-1 from baseline of the parent study over time in the OLE study (on-treatment estimand).
- The absolute change in Apo B/Apo A-1 from baseline of the parent study over time in the OLE study (on-treatment estimand).

# 2.1.4 Safety endpoints

The safety analysis will be based on the reported adverse events and other safety information, such as clinical laboratory data and vital signs.

### Observation period

The period of safety observation starts from the time when the patient gives informed consent and is divided into the following periods:

- The PRE-TREATMENT period: defined as the time from the signed informed consent date up to the time of first dose of alirocumab in the OLE study. The adverse events occurring during this period were to be reported and recorded in the parent study database. However, after the lock of parent study database, some exceptional pre-treatment adverse events have been recorded in the OLE study database with a start date in the parent study period.
- The treatment-emergent adverse event (TEAE) period: defined as the time from the first dose of alirocumab in the OLE study up to the day of last dose of alirocumab received in the OLE study + 70 days (10 weeks), as residual effect of alirocumab is expected until 10 weeks after the stop of alirocumab.

The TEAE period will include:

- The TREATMENT period defined as the time from the first dose of alirocumab in the OLE study up to the day of last dose of alirocumab received in the OLE study + 21 days.
- The POST-TREATMENT period: defined as the time starting the day after the end of TEAE period up to the end of study

The on-study observation period is defined as the time from first dose of alirocumab in the OLE study until the last protocol planned visit of the patient in the OLE study. The last protocol planned visit is defined as the safety follow-up call if done, else 10 weeks after last injection of alirocumab.

#### 2.1.4.1 Adverse events variables

Adverse events (including SAEs) and AESIs are recorded from the time of signed informed consent until the end of study. All AEs diagnosed by the Investigator, including CV events (irrespective of the result of the adjudication), will be reported and described.

All AEs will be coded to a "lowest level term (LLT)", "preferred term (PT)", "high level term (HLT)", "high level group term (HLGT)" and associated primary "system organ class (SOC)" using the version of MedDRA currently in effect at Sanofi at the time of database lock.

#### Adverse event observation period

- Pre-treatment AEs are AEs that developed or worsened or became serious during the pre-treatment period.
- Treatment-emergent adverse events are AEs that developed or worsened or became serious during the TEAE period.

• Post-treatment AEs are AEs that developed or worsened or became serious during the post-treatment period.

# Adverse events of special interest

AESIs are AEs (serious or non-serious) that need to be monitored, documented, and managed in a pre-specified manner described in the protocol. In this study, AESIs are the following (their complete descriptions are provided in the protocol):

- Local injection site reactions, selected using e-CRF specific tick box on the AE page;
- Allergic events:
  - General allergic events will be tabulated. Events will be selected using standardized MedDRA query (SMQ) "hypersensitivity" (broad and narrow) excluding the following preferred terms linked to local injection site reactions ("infusion site dermatitis", "infusion site hypersensitivity", "infusion site rash", "infusion site urticaria", "injection site dermatitis", "injection site hypersensitivity", "injection site rash", "injection site urticaria" and "injection site vasculitis");
  - General allergic events and local allergic reactions at IMP injection site will be described. This selection will be based on the above selection for general allergic event and on the following selection of PT from the symptoms complementary form for local injection site reaction ("Injection site dermatitis", "Injection site hypersensitivity", "Injection site oedema", "Injection site rash", "Injection site urticaria", "Injection site dermatitis", "Infusion site hypersensitivity", "Infusion site oedema", "Infusion site rash", "Infusion site urticaria", "Infusion site swelling");
- ALT≥3 ULN (if baseline ALT < ULN) or ALT ≥2 times the baseline value (if baseline ALT ≥ ULN), selected using laboratory data; The baseline that will be considered will be the OLE baseline of the current study
- Hemolytic anemia, selected using e-CRF specific tick box on the AE page and confirmed final diagnosis provided in the AE complementary form;
- Neurologic events selected using SMQs "demyelination" (broad and narrow), "peripheral neuropathy" (broad and narrow), and "Guillain-Barre syndrome" (broad and narrow) excluding the following preferred terms "acute respiratory distress syndrome", "asthenia", "respiratory arrest" and "respiratory failure";
- Neurocognitive events, selected using a company MedDRA query (CMQ), based on the following 5 HLGTs: "deliria (including confusion)", "cognitive and attention disorders and disturbances", "dementia and amnestic conditions", "disturbances in thinking and perception", and "mental impairment disorders";
- Neurocognitive events, selected using FDA proposed grouping including the PTs "Amnesia", "Amnestic disorder", "Anterograde Amnesia", "Behavioural and Psychiatric Symptoms of Dementia", "Change in sustained attention", "Cognitive Disorder", "Confusional State", "Delirium", "Dementia", "Dementia Alzheimer's type", "Dementia

with Lewy Bodies", "Disorientation", "Disturbance in attention", "Executive dysfunction", "Frontotemporal Dementia", "Illogical Thinking", "Impaired reasoning", "Incoherent", "Judgement impaired", "Memory Impairment", "Mental Impairment", "Mental Status Changes", "Mini Mental Status Examination Abnormal", "Presenile Dementia", "Retrograde Amnesia", "Senile Dementia", "Thinking Abnormal", "Transient Global Amnesia", "Vascular Dementia" and the LLTs "Mental State Abnormal Aggravated", "Thinking Slowed";

- Ophthalmologic events selected using SMQs "optic nerve disorders" (broad and narrow), "retinal disorders" (narrow), and "corneal disorders" (narrow);
- Overdose with IMP (symptomatic or asymptomatic), selected using appropriate MedDRA codes and the tick box "Overdose with IMP" in the AE complementary e-CRF form;
- Pregnancy of female patient/subject (including male subject's partner) selected using appropriate MedDRA codes.

Analyses of allergic, neurologic and ophthalmologic events will also be provided using the tick box on the e-CRF AE page as a second approach.

In addition the following grouping of events will be provided:

- Hepatic disorder events using SMQ "Hepatic disorder";
- Diabetes mellitus or diabetic complications using HLGT "Diabetes Complications" and HLT "Diabetes Mellitus", HLT "Carbohydrate tolerance analyses (incl diabetes)" excluding PT "Blood glucose decreased" and including PT "hyperglycemia".

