- Significant protocol deviation in the parent study based on the Investigator judgment, such as non-compliance by the patient.
- Adverse event leading to permanent discontinuation from parent study.
- Have any new condition or worsening of existing condition which in the opinion of the Investigator would make the patient unsuitable for enrollment, or could interfere with the patient participating in or completing the study.
- Positive pregnancy test at the end of treatment visit or end of study visit, according to the parent study the patient was originating from.
- Women of childbearing potential not willing to continue highlyeffective method of birth control and/or who are unwilling or unable to be tested for pregnancy.

Total expected number of patients Expected number of sites

Up to approximately 1,200 patients may be enrolled in the study.

Approximately 200 sites worldwide

	1					
STUDY TREATMENT(s)						
Investigational medicinal product:	alirocumab					
Formulation	Sterile alirocumab drug product supplied at a concentration of 75 mg/mL and 150 mg/mL in histidine, pH 6.0, polysorbate 20, and sucrose, both as 1 mL volume in an auto-injector.					
Route of administration	Subcutaneous (SC) injections in the abdomen, thigh or outer area of upper arm.					
Dose regimen	75 mg every 2 weeks OR					
	150 mg every 2 weeks					
Injection for training:	Placebo					
Formulation	Sterile solution consisting of histidine, pH 6.0, polysorbate 20, and sucrose, as 1 mL volume in an auto-injector.					
Route of administration	Subcutaneous (SC) injections in the abdomen, thigh or outer area of upper arm					
ENDPOINTS	The primary endpoint of this study is safety.					
	Safety Endpoints:					
	 Safety parameters (adverse events, laboratory data, vital signs) assessed throughout the OLE study. 					
	Efficacy Endpoints of interest include:					
	 Calculated serum LDL-C values and percent changes from baseli of the parent study (EFC 12492, R727-CL-1112, EFC 12732 or LTS11717) over time in this study. 					
	 Proportion of patients achieving an LDL-C < 100 mg/dL (2.59 mmol/l) over time in this study. 					
	 Proportion of patients achieving an LDL-C < 70 mg/dL (1.81 mmol/L) over time in this study. 					
	 Proportion of patients with LDL-C <70 mg/dL (1.81 mmol/L) and/or ≥50% reduction from baseline of the parent study in LDL-C (if LDL-C ≥70 mg/dL [1.81 mmol/L]) over time in this study. 					

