 - An overdose (accidental or intentional) is an event suspected by the Investigator or spontaneously notified by the patient (not based on systematic injection counts) and defined as at least twice of the intended dose within the intended therapeutic interval (ie, 2 or more injections from the treatment kit are administered in <7 calendar days); to be reported using the corresponding screens in the e-CRF using the Term 'Symptomatic OVERDOSE (accidental [or intentional])'. The patient should be monitored and appropriate symptomatic treatment instituted.
 - The circumstances of the overdose should be clearly specified in the verbatim.
- Neurologic Events
 - Neurologic Events that require additional examinations/procedures and/or referral to a specialist should be reported immediately (ie, within 24 hours), as per SAEs notification described in Section 10.4.1.3, even if not fulfilling a seriousness criterion.
- Ophthalmologic Events
 - Ophthalmologic Events that require additional examinations/procedures and/or referral to a specialist should be reported immediately (ie, within 24 hours), as per SAEs notification described in Section 10.4.1.3, even if not fulfilling a seriousness criterion.

10.4.4.2 AESI without immediate notification:

• Asymptomatic Overdose with IMP

An overdose is defined in the above section.

In case of an asymptomatic overdose with IMP, the event should be reported using the corresponding screens in the e-CRF using the Term "Asymptomatic OVERDOSE (accidental [or intentional])". The patient should be monitored for any adverse events and treated, as needed

• Local injection site reactions (see section 10.6.1)

Local injection site reactions that are considered as non-allergic events and that are related to the IMP injection, as opposed to another injectable agent, should be further characterized by evaluating the related symptoms that comprise an injection site reaction such as but not limited to redness, pain, etc (See Appendix F). Special e-CRF screens will need to be completed. If such an AE were to occur, then do not report the individual components of the reaction but rather the term "local injection site reaction", with the individual components being described in the specific e-CRF screen.

• Allergic events not referred for consultation with another physician (see above section)

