10.6.2 Allergic adverse events

Specific e-CRF screens are to be filled in to assess allergic reactions or allergic-like reactions that may occur during the clinical studies conducted with alirocumab.

10-Jul-2015 Version number: 1

Sometimes transient injection site reactions, irritant in nature, may occur, requiring no intervention and being of dubious significance. These reactions would not be considered to be allergic reactions.

Adverse events that may constitute an allergic reaction (eg, generalized itch, nasal itch, swelling at injection site, flushing, hives, swelling at lips, eyes, face, tongue, hands, feet, lump in throat, difficulty to swallow, hoarseness, change in pitch of voice, incapacity to speak, wheezing, chest tightness, stridor, etc) should be considered to be reported on the General Allergic Reaction and/or Local Injection Site Reaction Complementary Form (see Section 10.4.4).

Adverse events that are obviously not of allergic origin (eg, local injection site reactions) should only be recorded on the Local Injection Site Reaction Complementary Form. However, injection site reactions which progress/expand/worsen/etc should be evaluated as recommended in 10.6.2.1 and General Allergic Reaction Complementary form should be completed. (See Sections 10.4.4)

The IMP should be immediately interrupted (temporarily discontinued) if there is a suspicion of an allergic event related to IMP. See Section 10.3.1 for further information on treatment interruption and Section 10.3.3 for criteria for permanent treatment discontinuation.

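### The term list for local allergic reactions includes infusion-site swelling but omits injection-site swelling, for a product given only by subcutaneous injection

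*SAP*

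**What the plan says.** SAP 2.1.4.1, under adverse events of special interest, sets up two allergic selections from coded terms.

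- **General allergic events.** These come from the hypersensitivity standardized MedDRA query (SMQ), broad and narrow, less nine terms tied to local reactions. The nine end with "injection site rash', 'injection site urticaria' and 'injection site vasculitis".
- **General allergic events plus local allergic reactions at the injection site.** This is the first selection plus the "following selection of PT from the symptoms complementary form for local injection site reaction". The second half of the added list reads "Injection site urticaria', 'Injection site dermatitis', 'Infusion site hypersensitivity', 'Infusion site oedema', 'Infusion site rash', 'Infusion site urticaria', 'Infusion site swelling".

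The same section states that analyses of allergic events "will also be provided using the tick box on the e-CRF AE page as a second approach". SAP 2.4.5.1 carries the groupings into the summaries of treatment-emergent events, serious events and events leading to discontinuation.

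The protocol summary gives the route as "Subcutaneous (SC) injections in the abdomen, thigh or outer area of upper arm". Protocol 10.6.2 begins its examples with "Adverse events that may constitute an allergic reaction (eg, generalized itch, nasal itch, swelling at injection site". The same section says of transient, irritant injection-site reactions: "These reactions would not be considered to be allergic reactions". For local reactions considered non-allergic, Protocol 10.4.4.2 tells sites "do not report the individual components of the reaction but rather the term 'local injection site reaction" and to describe the components on a dedicated e-CRF screen.

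**The concern.** Assessing long-term safety is the primary objective, and allergic events are among the events of special interest. A preferred-term list is an operative rule: it is programmed literally, and a term that is not on it is not picked up by it.

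The added list exists to bring local allergic reactions into the combined selection. For swelling, it carries only the infusion-site form. No infusions are given in this study, so that is the form least likely to be used. The injection-site form, which matches one of the protocol's own examples, is absent. If the list is programmed as it stands, the combined grouping could understate local allergic reactions.

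**Working it through.** There is no sample size, error rate or event count to recompute. The check compares the two lists in SAP 2.1.4.1 and sets them against the protocol.

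**Step 1. Lay out the added list by reaction type.**

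| Reaction type | Injection-site term | Infusion-site term |
|---|---|---|
| Hypersensitivity | listed | listed |
| Oedema | listed | listed |
| Rash | listed | listed |
| Urticaria | listed | listed |
| Dermatitis | listed twice | not listed |
| Swelling | **not listed** | listed |

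Entries: 6 injection-site (one of them a repeat) + 5 infusion-site = 11. Distinct terms: 11 − 1 = 10, of which 5 are injection-site and 5 infusion-site. Four of the six reaction types have both forms. Swelling is the only type without its injection-site form.

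**Step 2. Is the asymmetry deliberate or a slip?** The repeated *Injection site dermatitis* stands at the head of the infusion-site run, where *Infusion site dermatitis* would be expected. The nine-term exclusion list in the same section has dermatitis in both forms. This suggests that the added list was not proofread. It has no effect on counts: repeating a term does not change which events are selected, and infusion-site terms are not expected with a subcutaneous product. The documents give no reason for keeping infusion-site swelling and both oedema terms while leaving out injection-site swelling. If swelling had been judged too non-specific, the infusion-site form should have gone too.

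**Step 3. By what routes could injection-site swelling enter the combined selection?**

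- *Through the added list.* The list is drawn from the symptoms form. Swelling recorded there and coded to *Injection site swelling* finds no match.
- *Through the SMQ.* The term is not among the nine exclusions, so it could enter this way if the SMQ contains it and it was reported as an adverse event term. The documents do not give the SMQ contents. For reactions considered non-allergic, Protocol 10.4.4.2 sends the components to the separate screen, so they would not normally be available as adverse event terms.

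**Step 4. Can the shortfall be sized?** No. That would need the items on the form and how they are coded, the SMQ contents, and the frequency of injection-site swelling. None of these is given.

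**The case against.** The strongest reply is that the effect depends on sources not shown. Swelling is missed only if the form yields *Injection site swelling* as a term separate from *Injection site oedema*, and only if the SMQ does not supply it. If swelling on the form is coded to *Injection site oedema*, which is listed, nothing is lost. This stands, and it limits the claim to what the added list does as written.

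The second reply concerns specificity. Protocol 10.6.2 says only that such events may be allergic, it sets irritant reactions apart, and it uses local injection site reactions as its example of events plainly not of allergic origin. A term list applies no clinical judgement, so adding a non-specific sign trades a possible under-count for a possible over-count. This stands as a cost of the fix. It does not explain the omission, because both oedema terms and infusion-site swelling are on the list.

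The third reply is that little depends on this grouping. The study is uncontrolled, the output is descriptive, and a tick-box allergic analysis is already planned. That also stands, and it sets the severity.

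**Conclusion.** The omission is certain from the text. Its consequence is conditional: swelling recorded on the symptoms form and coded to *Injection site swelling* would not enter the combined selection through the added list. This assumes that the list is programmed literally and that the term is available in the MedDRA version used, as its infusion-site counterpart is taken to be. The size of any under-count cannot be computed.

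The point is minor. It touches one descriptive grouping of events of special interest. Three planned outputs partly mitigate it: the local-reaction selection by tick box, the allergic analysis by tick box, and the tabulation of symptom intensity for local reactions in SAP 2.4.5.1. None of them corrects the combined selection itself.

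A reader might go further in three directions that the documents do not support:

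- *That allergic swelling will be lost from the safety report.* The form and SMQ contents are not shown, and the tick-box analyses do not depend on this list.
- *That the all-event tables by preferred term would show it anyway.* Swelling recorded only on the symptoms form would not appear there under that term, given the instruction in Protocol 10.4.4.2.
- *That* Injection site vasculitis*, excluded from the general selection and not added back, is a second error.* It may simply not be an item on the form, and the documents cannot settle this.

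**What to change.** In SAP 2.1.4.1, add *Injection site swelling* to the added list and replace the second *Injection site dermatitis* with *Infusion site dermatitis*. The list then has 12 entries, all distinct: six reaction types in two forms each. If the asymmetry was intended, one sentence giving the reason would serve instead.

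The cost is a few words in the SAP and an updated term list for programming. The downside is that some irritant, non-allergic swelling may enter the combined count. To let readers judge this, present the already planned tick-box allergic analysis beside the combined selection. No new data collection is needed.
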